9.8 Quality control

Two reviewers independently extract data and study characteristics from each citation, and any discrepancies between reviewers will be reconciled by a third independent reviewer. Citations that do not match the eligibility criteria will be excluded at this stage; whereas unclear citations will be included.

The Preferred Reporting Items for Systematic reviews and Meta-Analysis (PRISMA) will be employed for reporting of included studies

Newcastle-Ottawa scale (NOS) will be used to assess and appraise the methodological quality of included studies

9.9 Limitations of the research methods

- There may have potential biases (recall and publication bias) inherent in retrospective casecontrol design. These types of study may also have higher sensitivity to detect low-frequency defects
- Included studies lacked data evaluating the relationship between dosage and duration of medication and teratogenic effects, which could affect the results of the study.
- Confounding factors assessed and described in the published sources could be an explaining factor for clinical heterogeneity, which includes the decision for a specific treatment / administration of glucocorticosteroids, but also other factors could be a reason for heterogeneityRange of dosages used is relatively wide in included studies which may have an influence on the results
- Conditions of skin, size of the skin surface treated and the part of the body where it is applied were not reported in all studies which may have an influence on the absorption of corticosteroids which may alter effect outcomes

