Bayer's glucocorticoid product, Nerisona (INN) Diflucortolone valerate (for topical use) is contraindicated for use during pregnancy. In the scope of a regulatory procedure, the French Health Authority has requested Bayer to conduct a meta-analysis encompassing all studies investigating a possible increase in the risk of cleft palates in neonates of women treated with glucocorticoids during the first trimester of pregnancy.

In response to this request, a systematic literature review (SLR) was conducted to identify relevant studies evaluating the potential association between the exposure to glucocorticoids and the occurrence of orofacial cleft. Due to the heterogeneity findings in the 18 selected publications, a meta-analysis of their results was deemed as warranted and will be conducted as originally requested. Since this analysis will evaluate the risks of a medicinal product class used in a patient population for which safety information is limited or missing (e.g. pregnant women), it is considered as a Post Authorization Safety Study (PASS), in accordance with the European Medicine Agency Guideline on good pharmacovigilance practices (GVP) Module VIII – Post -authorisation safety studies (Rev 3) (18).

Of note, a meta-analysis for topical administration of corticosteroids during early pregnancy is not published. Nevertheless, a meta-analysis (16) was identified in the SLR that discusses effect of use of corticosteroids during early pregnancy without specifying the route of administration. This meta-analysis also has some shortcomings such as:

- Relationship between dosage and duration of medication were not examined in the included studies that could affect their results
- Confounding factors, such as race, maternal age, level of education, economic and social status, smoking, chances of repetitive enrollment of some patients in different studies were not addressed
- Dosage of glucocorticoid was not discussed
- Recall and publication bias due to retrospective design

Thus, further analyses are warranted to investigate a concrete association between the exposure to glucocorticoids and the developmental orofacial cleft. The current meta-analysis aims to also address some of the shortcoming of the existing meta-analysis such as the confounder effect by subgroup analyses. However, not all shortcomings will be addressed due to lack of data availability in the published literature.

8. Research questions and objectives

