9.2.1 Selection criteria used for the Systematic Literature Review (SLR)

The inclusion and exclusion criteria used for the selection of studies as well as detailed methodology of the systematic literature review are provided in the Appendix 1.

No time period restriction was used. The systematic literature review was conducted to identify all studies (including observational studies and clinical trials) published till 25 June 2018 (search date). In addition, there were no restrictions to the route of administration.

Only 18 studies were shortlisted based on the inclusion criteria. All of the 18 studies were observational studies while no clinical trials were identified that met the inclusion criteria.

The selection criteria utilized in the SLR were the following:

Inclusion criteria

- Population: Pregnant women
- Intervention: Any glucocorticoid or corticosteroid or steroids use irrespective of mode of administration
- Comparator: Any/none
- Outcomes: Incidence/ risk of cleft lip/palate in infants
- Study Design:
 - Meta-analysis and systematic literature reviews
 - Observational studies (such as cohort study, case-control study, registries data)
 - Clinical trials Phase IIb, III, and IV
 - Conference abstracts/posters
- Time period: No time period restriction
- Geography: No geography restriction

Exclusion criteria

- Population: Nonpregnant women
- Intervention: Drugs other than glucocorticoid or corticosteroid or steroid
- Outcomes: Incidence/ risk of cleft lip/palate in infants
- Study Design:
 - Animal Study

- In vitro studies
- o Editorial, letters, comment
- Clinical trials Phase I or preclinical
- Case reports, case series
- o Reviews
- Studies focusing on:
 - Diagnosis and surgical procedure for cleft repair
 - o Impact of Increased internal corticosteroids due to stress
 - The relationship between genetic mutations and cleft patients
 - Adverse events for other drugs
 - Safety profiles of glucocorticoid or corticosteroid

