	9.3.1 Exposure? (e.g. WHO Drug Dictionary, Anatomical Therapeutic Chemical (ATC) Classification System)		\boxtimes		
	9.3.2 Outcomes? (e.g. International Classification of Diseases (ICD), Medical Dictionary for Regulatory Activities (MedDRA))		\boxtimes		
	9.3.3 Covariates and other characteristics?		\boxtimes		
9.4	Is a linkage method between data sources described? (e.g. based on a unique identifier or other)			\square	

The data sources for the study are the selected literature publications.

Section 10: Analysis plan	Yes	No	N/A	Section Number
10.1 Are the statistical methods and the reason for their choice described?	\boxtimes			9.7
10.2 Is study size and/or statistical precision estimated?		\boxtimes		
10.3 Are descriptive analyses included?	\boxtimes			9.7
10.4 Are stratified analyses included?	\boxtimes			9.7
10.5 Does the plan describe methods for analytic control of confounding?		\boxtimes		
10.6 Does the plan describe methods for analytic control of outcome misclassification?		\boxtimes		
10.7 Does the plan describe methods for handling missing data?		\boxtimes		
10.8 Are relevant sensitivity analyses described?				9.7

Comments:

The meta-analysis assumes that the selected literature publications fulfill scientific quality standards to address the study objectives.

Section 11: Data management and quality control	Yes	No	N/A	Section Number
11.1 Does the protocol provide information on data storage? (e.g. software and IT environment, database maintenance and anti-fraud protection, archiving)		\boxtimes		
11.2 Are methods of quality assurance described?	\boxtimes			9.8
11.3 Is there a system in place for independent review of study results?		\boxtimes		

Comments:

This is a meta-analysis of published literature. Study data will be stored in accordance with quality procedures.

Section 12: Limitations	Yes	No	N/A	Section Number
12.1 Does the protocol discuss the impact on the study results of:				
12.1.1 Selection bias?		\square		
12.1.2 Information bias?		\square		9.9
12.1.3 Residual/unmeasured confounding? (e.g. anticipated direction and magnitude of such biases, validation sub-study, use of validation and external data, analytical methods).				
12.2 Does the protocol discuss study feasibility? (e.g. study size, anticipated exposure uptake, duration of follow-up in a cohort study, patient recruitment, precision of the estimates)		\boxtimes		

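### The protocol acknowledges possible recall bias in case-control studies but fixes one fixed-effect pool of all designs, with no split by design or exposure source and no stated analytic use of the quality score

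*Protocol*

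**What the plan says.** Section 7 lists weaknesses of the published meta-analysis, among them "Recall and publication bias due to retrospective design". It then states an aim: "The current meta-analysis aims to also address some of the shortcoming of the existing meta-analysis such as the confounder effect by subgroup analyses". It qualifies this at once: "However, not all shortcomings will be addressed due to lack of data availability in the published literature".

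Section 9.9 turns to the present work: "There may have potential biases (recall and publication bias) inherent in retrospective casecontrol design".

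Under 9.2.1, cohort, case-control and registry studies are all eligible, and "All of the 18 studies were observational studies". Section 9.3.3 names two covariates, potency and route. Section 9.7 sets a fixed-effect inverse-variance model with a common underlying effect, and subgroups by route, cleft type and potency. It also sets one sensitivity analysis, which repeats the pool without outliers if heterogeneity is high; no threshold is given.

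On quality, 9.8 says: "Newcastle-Ottawa scale (NOS) will be used to assess and appraise the methodological quality of included studies". The comment under Section 10 of the Annex 2 checklist says: "The meta-analysis assumes that the selected literature publications fulfill scientific quality standards to address the study objectives". In the same checklist, item 7.3, on whether information bias is addressed, is marked No.

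**The concern.** Recall bias is systematic. If mothers of affected infants remember drug use more completely than mothers of healthy infants, the odds ratio of a case-control study rises, and pooling more such studies does not remove the excess. A model that attributes all differences between studies to sampling error has no place for it, and inverse-variance weights take no account of it.

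The conflict in the literature is the reason for the study: section 7 sets reports of a 3-6 fold risk beside reports of none. One obvious candidate explanation is how exposure was ascertained. The listed analyses provide no estimate by design, so the report could discuss that explanation but would have no figures to test it. Publication bias, named in the same sentence of 9.9, gets a funnel plot and Egger's test; recall bias gets no analysis.

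**Working it through.** The protocol gives no figure to reproduce here. The check has two parts: what the text fixes, and an illustration in which every numerical input is an assumption.

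**1. Does any listed analysis separate designs?**
- Covariates (9.3.3): potency, route. No.
- Subgroups (9.7): route, cleft type, potency. No.
- Sensitivity analysis (9.7): outliers removed, conditional on high heterogeneity. No.
- Newcastle-Ottawa scale (9.8): applied, but no weighting, exclusion, stratum or sensitivity analysis is tied to it.

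**2. One case-control study with differential recall.** Assume a true odds ratio of 1, true exposure p = 0.03 in both groups and no false reports. Let Sc and S0 be the proportions of exposed case and control mothers who report use.

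Observed OR = [p·Sc/(1 − p·Sc)] / [p·S0/(1 − p·S0)]

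- Sc = 0.8, S0 = 0.7: 0.02459/0.02145 = 1.15
- Sc = 0.9, S0 = 0.7: 0.02775/0.02145 = 1.29
- Sc = 0.9, S0 = 0.5: 0.02775/0.01523 = 1.82

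Exposure prevalence hardly matters: with Sc = 0.9 and S0 = 0.7, p from 0.01 to 0.05 gives 1.29 to 1.30.

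**3. Carry-over to the pool.** If case-control studies with biased odds ratio B carry a share w of the weight and the other studies are unbiased at 1, the pooled OR is exp(w·ln B).
- B = 1.3: 1.05, 1.14, 1.23 for w = 0.2, 0.5, 0.8
- B = 1.5: 1.08, 1.22, 1.38 for the same shares

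**4. Would the heterogeneity condition catch it?** Assume 9 case-control and 9 cohort studies, each with the same standard error s of the log odds ratio. Then E[Q] = 17 + 18·(ln B/2)²/s², approximate I² = (E[Q] − 17)/E[Q], and the lower 95% limit is exp(ln B/2 − 1.96·s/√18).
- B = 1.5: 18·(0.4055/2)² = 0.740. For s = 0.2, 0.3, 0.4, E[Q] = 35.5, 25.2, 21.6; I² = 52%, 33%, 21%; lower limit = 1.12, 1.07, 1.02.
- B = 1.3: 18·(0.2624/2)² = 0.310. For the same s, E[Q] = 24.7, 20.4, 18.9; I² = 31%, 17%, 10%; lower limit = 1.04, 0.99, 0.95.

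Under these assumptions, recall bias alone can put the pooled interval above 1 while heterogeneity is low or moderate. Where heterogeneity is larger (52%), the analysis it might trigger removes outliers, not a design.

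**The case against.** - **The statistical analysis plan may cover it.** A plan dated 10 September 2018 exists and is not shown, and extra subgroups often belong there. This has weight for detail. But the protocol, in version 1.2 of 16 November 2018, itself lists the covariates, the subgroups and the sensitivity analysis, and none touches the bias it names.
- **No promise is broken.** A reader might infer from section 7 that the protocol undertook to remove recall bias. It did not: it undertakes to address some shortcomings, gives confounding as its only example, and says others will remain. Section 9.9 says only that bias may be present. This objection stands. The reason given for the gaps, lack of published data, fits study design poorly, since a paper normally states its design.
- **The appraisal is not empty.** A reader might infer that the Annex 2 comment makes the Newcastle-Ottawa scale pointless. A reported appraisal still informs interpretation, and Annex 2 describes the checklist as a supporting document. What stands is that the score has no stated use in the analysis and that the two statements need reconciling.
- **Discussion is promised.** Section 9.7 says departures from the common-effect assumption, and plausible reasons for high heterogeneity, will be discussed. Design can be raised there, but no design-specific estimate is planned.
- **Exposure is a redeemed prescription under 9.3.1**, which is not maternal recall. If that held for all 18 studies, the recall concern in 9.9 would not arise. The two sections pull apart, which itself favours a split by exposure source.
- **Direction and size.** Under-reporting that is equal in cases and controls pulls the odds ratio towards 1. Even 1.82 is well short of a 3-6 fold risk, so the illustration does not explain those reports.

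**Conclusion.** The point holds in this form: the protocol acknowledges a possible design-related bias, then fixes an analysis that neither separates designs nor gives the quality score a stated role. It should be corrected before the pooled odds ratio is interpreted.

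The size is unknown. The numbers of case-control and cohort studies, and how many rely on maternal report, are not in the text available. The range 1.15 to 1.82 describes one case-control study under assumed recall. The pooled values (1.05 to 1.38) and the I² figures rest further on assumed weights, an assumed 9/9 split and equal standard errors. They show that the mechanism could matter without triggering the planned check, not that it operates here.

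A reader might also infer that, if the strata disagree, the conclusion should rest on exposure recorded before birth. The documents do not support such a rule. A redeemed prescription does not prove use, and the resulting misclassification typically pulls towards 1, the unsafe direction for a safety question. Section 9.9 also credits case-control studies with possibly greater sensitivity for low-frequency defects.

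**What to change.** - **Section 9.7, subgroup:** add study design or exposure source as a prespecified subgroup, with exposure recorded before the outcome set against exposure reported by the mother afterwards. Report it whatever the heterogeneity, show both pooled odds ratios, and discuss any disagreement in the conclusion.
- **Section 9.7, sensitivity:** add one unconditional sensitivity analysis based on the Newcastle-Ottawa assessment, with the rule fixed before the results are seen.
- **Section 9.8 and Annex 2:** state how the appraisal enters the analysis, and reconcile this with the comment that quality is assumed.

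The cost is two further analyses with their forest plots, from information normally available in the papers being appraised. The real downside is precision: each stratum has fewer than 18 studies and so a wider interval.

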9.10 Other aspects

Not applicable.

10. Protection of human subjects

This study is based on published data only. No data with personal identifiable/sensitive information will be used. All data are aggregated and anonymised. GDPR is not applicable and the analyses of data in this way is not covered and justified in the most recent release of the Declaration of Helsinki.

11. Management and reporting of adverse events/adverse reactions

As per the EMA Guideline on Good Pharmacovigilance Practices (Module VI–Management and reporting of adverse reactions to medicinal products [Revision 1]), individual reporting of adverse reactions is not required for non-interventional study designs that are based on secondary use of data (19). Reports of adverse events/reactions will be summarized in the study report (European Medicines Agency 2014).

12. Plans for disseminating and communicating study results

As this meta-analysis is conducted in response to a query from French Health Authority Format, the content of the study protocol for post-authorization safety studies (PASS), as specified in Art 36 to 38 and Art 40 of the Commission Implementing Regulation (EU) No 520/2012 was used. European Medicines Agency guidance for the format and content of the final study report of non-interventional post-authorization safety studies was also used to develop the protocol for current meta-analysis.

The results of this meta-analysis are intended to be published in a peer-reviewed journal and as abstracts/presentations at medical congresses under the oversight of the MAH. Current guidelines and recommendation on good publication practice will be followed (e.g. GPP2 Guidelines (20)).

13. References

Annex 1: List of stand-alone documents

Table 2: List of stand-alone documents

Document Name	Final version and date (if available)*		
Systematic Literature Review Report*	09 JUL 2018		
SAP	10 SEP 2018		

*Please refer to Appendix 3.

Annex 2: ENCePP checklist for post-authorization safety study (PASS) protocols

Please check for the current version of the ENCePP checklist for study protocols at http://www.encepp.eu/standards_and_guidances/checkListProtocols.shtml.

Doc.Ref. EMA/540136/2009

European Network of Centres for Pharmacoepidemiology and Pharmacovigilance

ENCePP Checklist for Study Protocols (Revision 4)

Adopted by the ENCePP Steering Group on 15/10/2018

The European Network of Centres for Pharmacoepidemiology and Pharmacovigilance (ENCePP) welcomes innovative designs and new methods of research. This Checklist has been developed by ENCePP to stimulate consideration of important principles when designing and writing a pharmacoepidemiological or pharmacovigilance study protocol. The Checklist is intended to promote the quality of such studies, not their uniformity. The user is also referred to the ENCePP Guide on Methodological Standards in Pharmacoepidemiology, which reviews and gives direct electronic access to guidance for research in pharmacoepidemiology and pharmacovigilance.

For each question of the Checklist, the investigator should indicate whether or not it has been addressed in the study protocol. If the answer is "Yes", the section number of the protocol where this issue has been discussed should be specified. It is possible that some questions do not apply to a particular study (for example, in the case of an innovative study design). In this case, the answer 'N/A' (Not Applicable) can be checked and the "Comments" field included for each section should be used to explain why. The "Comments" field can also be used to elaborate on a "No" answer.

This Checklist should be included as an Annex by marketing authorisation holders when submitting the protocol of a non-interventional post-authorisation safety study (PASS) to a regulatory authority (see the Guidance on the format and content of the protocol of non-interventional post-authorisation safety studies). The Checklist is a supporting document and does not replace the format of the protocol for PASS presented in the Guidance and Module VIII of the Good pharmacovigilance practices (GVP).

Study title:

Risk association of orofacial cleft and Glucocorticoids exposure during pregnancy: a metaanalysis

EU PAS Register[®] number: Study reference number (if applicable): Impact#20638

Sect	tion 1: Milestones	Yes	No	N/A	Section Number
1.1	Does the protocol specify timelines for				6
	1.1.1 Start of data collection ¹	\square			
	1.1.2 End of data collection ²	\square			
	1.1.3 Progress report(s)		\boxtimes		
	1.1.4 Interim report(s)		\boxtimes		
	1.1.5 Registration in the EU PAS Register $^{\scriptscriptstyle(\!R\!)}$	\square			

¹ Date from which information on the first study is first recorded in the study dataset or, in the case of secondary use of data, the date from which data extraction starts. ² Date from which the analytical dataset is completely available.

30 Churchill Place • Canary Wharf • London E14 5EU • United KingdomTelephone [name] [contact]E-mail: [contact] www.encepp.eu

Section 1: Milestones	Yes	No	N/A	Section Number
1.1.6 Final report of study results.	\boxtimes			6

EU PAS registration is ongoing.

NOCTION	Section 2: Deceased question						
Section	2: Research question	res	NO	N/A	Section Number		
2.1 Doo obj	es the formulation of the research question and jectives clearly explain:	\square					
2.1	1.1 Why the study is conducted? (e.g. to address an important public health concern, a risk identified in the risk management plan, an emerging safety issue)	\boxtimes			7 and 8		
2.1	1.2 The objective(s) of the study?	\square					
2.1	1.3 The target population? (i.e. population or subgroup to whom the study results are intended to be generalised)	\bowtie					
2.1	1.4 Which hypothesis(-es) is (are) to be tested?		\square				
2.1	1.5 If applicable, that there is no a priori hypothesis?			\square			

Comments:

The study is not testing any hypothesis.

Sect	ion 3: Study design	Yes	No	N/A	Section Number
3.1	Is the study design described? (e.g. cohort, case- control, cross-sectional, other design)	\boxtimes			9
3.2	Does the protocol specify whether the study is based on primary, secondary or combined data collection?	\boxtimes			9
3.3	Does the protocol specify measures of occurrence? (e.g., rate, risk, prevalence)	\boxtimes			9
3.4	Does the protocol specify measure(s) of association? (e.g. risk, odds ratio, excess risk, rate ratio, hazard ratio, risk/rate difference, number needed to harm (NNH))	\boxtimes			9
3.5	Does the protocol describe the approach for the collection and reporting of adverse events/adverse reactions? (e.g. adverse events that will not be collected in case of primary data collection)				11

Comments:

The study is a meta-analysis of published literature, thus uses secondary data. Reporting of findings will be done in the in the study report in aggregated form.

Sec t	ion 4: Source and study populations	Yes	No	N/A	Section Number
4.1	Is the source population described?	\square			
4.2	Is the planned study population defined in terms of:				
	4.2.1 Study time period	\square			

Sect	tion 4: Source and study populations	Yes	No	N/A	Section Number
	4.2.2 Age and sex		\square		
	4.2.3 Country of origin		\bowtie		9.1, 9.2
	4.2.4 Disease/indication		\bowtie		
	4.2.5 Duration of follow-up		\square		
4.3	Does the protocol define how the study population will be sampled from the source population? (e.g. event or inclusion/exclusion criteria)	\boxtimes			9.1, 9.2

The study is a meta-analysis of published literature. The search criteria for inclusion are described in the protocol.

Sect	ion 5: Exposure definition and measurement	Yes	No	N/A	Section Number
5.1	Does the protocol describe how the study exposure is defined and measured? (e.g. operational details for defining and categorising exposure, measurement of dose and duration of drug exposure)	\boxtimes			9.2.1
5.2	Does the protocol address the validity of the exposure measurement? (e.g. precision, accuracy, use of validation sub-study)		\boxtimes		
5.3	Is exposure categorised according to time windows?	\boxtimes			9.2.1
5.4	Is intensity of exposure addressed? (e.g. dose, duration)		\boxtimes		
5.5	Is exposure categorised based on biological mechanism of action and taking into account the pharmacokinetics and pharmacodynamics of the drug?		\boxtimes		
5.6	Is (are) (an) appropriate comparator(s) identified?	\square			

Comments:

The study does not investigate the validity of exposure assessment, assumes that the selected literature publications fulfill quality standards to address the study objectives. Non-exposure to treatment is deemed the most appropriate comparator.

Sect	ion 6: Outcome definition and measurement	Yes	No	N/A	Section Number
6.1	Does the protocol specify the primary and secondary (if applicable) outcome(s) to be investigated?	\boxtimes			8
6.2	Does the protocol describe how the outcomes are defined and measured?	\boxtimes			9.3.2
6.3	Does the protocol address the validity of outcome measurement? (e.g. precision, accuracy, sensitivity, specificity, positive predictive value, use of validation sub- study)		\boxtimes		

Sect	ion 6: Outcome definition and measurement	Yes	No	N/A	Section Number
6.4	Does the protocol describe specific outcomes relevant for Health Technology Assessment? (e.g. HRQoL, QALYs, DALYS, health care services utilisation, burden of disease or treatment, compliance, disease management)		\boxtimes		

The study is a meta-analysis of literature. The outcome investigated is orofacial cleft in the offspring of mother exposed to corticosteroids during the first trimester of pregnancy.

Sect	ion 7: Bias	Yes	No	N/A	Section Number
7.1	Does the protocol address ways to measure confounding? (e.g. confounding by indication)		\boxtimes		
7.2	Does the protocol address selection bias? (e.g. healthy user/adherer bias)		\boxtimes		
7.3	Does the protocol address information bias? (e.g. misclassification of exposure and outcomes, time-related bias)		\boxtimes		

Comments:

Reporting or publication bias will be assessed by using the funnel plot (symmetry or asymmetry) and it again confirmed by using the Egger's test (in case of asymmetry funnel plot). Further, any outliers in the effect size will be determined by Galbraith plot

Sect	ion 8: Effect measure modification	Yes	No	N/A	Section Number
8.1	Does the protocol address effect modifiers? (e.g. collection of data on known effect modifiers, sub-group analyses, anticipated direction of effect)	\boxtimes			9.7

Comments:

Sect	ion 9: Data sources	Yes	No	N/A	Section Number
9.1	Does the protocol describe the data source(s) used in the study for the ascertainment of:				
	9.1.1 Exposure? (e.g. pharmacy dispensing, general practice prescribing, claims data, self-report, face-to-face interview)		\boxtimes		
	9.1.2 Outcomes? (e.g. clinical records, laboratory markers or values, claims data, self-report, patient interview including scales and questionnaires, vital statistics)		\boxtimes		
	9.1.3 Covariates and other characteristics?	\square			9.3.3
9.2	Does the protocol describe the information available from the data source(s) on:				
	9.2.1 Exposure? (e.g. date of dispensing, drug quantity, dose, number of days of supply prescription, daily dosage, prescriber)		\boxtimes		
	9.2.2 Outcomes? (e.g. date of occurrence, multiple event, severity measures related to event)		\boxtimes		

Sect	ion 9: Data sources	Yes	No	N/A	Section Number
	9.2.3 Covariates and other characteristics? (e.g. age, sex, clinical and drug use history, co-morbidity, co-medications, lifestyle)		\boxtimes		
9.3	Is a coding system described for:				
	9.3.1 Exposure? (e.g. WHO Drug Dictionary, Anatomical Therapeutic Chemical (ATC) Classification System)		\boxtimes		
	9.3.2 Outcomes? (e.g. International Classification of Diseases (ICD), Medical Dictionary for Regulatory Activities (MedDRA))		\boxtimes		
	9.3.3 Covariates and other characteristics?		\boxtimes		
9.4	Is a linkage method between data sources described? (e.g. based on a unique identifier or other)			\square	

The data sources for the study are the selected literature publications.

Section 10: Analysis plan	Yes	No	N/A	Section Number
10.1 Are the statistical methods and the reason for their choice described?	\boxtimes			9.7
10.2 Is study size and/or statistical precision estimated?		\boxtimes		
10.3 Are descriptive analyses included?	\boxtimes			9.7
10.4 Are stratified analyses included?	\boxtimes			9.7
10.5 Does the plan describe methods for analytic control of confounding?		\boxtimes		
10.6 Does the plan describe methods for analytic control of outcome misclassification?		\boxtimes		
10.7 Does the plan describe methods for handling missing data?		\boxtimes		
10.8 Are relevant sensitivity analyses described?				9.7

Comments:

The meta-analysis assumes that the selected literature publications fulfill scientific quality standards to address the study objectives.

Section 11: Data management and quality control	Yes	No	N/A	Section Number
11.1 Does the protocol provide information on data storage? (e.g. software and IT environment, database maintenance and anti-fraud protection, archiving)		\boxtimes		
11.2 Are methods of quality assurance described?	\boxtimes			9.8
11.3 Is there a system in place for independent review of study results?		\boxtimes		

Comments:

This is a meta-analysis of published literature. Study data will be stored in accordance with quality procedures.

Section 12: Limitations	Yes	No	N/A	Section Number
12.1 Does the protocol discuss the impact on the study results of:				
12.1.1 Selection bias?		\square		
12.1.2 Information bias?		\square		9.9
12.1.3 Residual/unmeasured confounding? (e.g. anticipated direction and magnitude of such biases, validation sub-study, use of validation and external data, analytical methods).				
12.2 Does the protocol discuss study feasibility? (e.g. study size, anticipated exposure uptake, duration of follow-up in a cohort study, patient recruitment, precision of the estimates)		\boxtimes		

The feasibility of this meta-analysis has been addressed by a previous systematic literature review. Publication bias is discussed in section 9.9

Section 13: Ethical/data protection issues	Yes	No	N/A	Section Number
13.1 Have requirements of Ethics Committee/ Institutional Review Board been described?		\boxtimes		
13.2 Has any outcome of an ethical review procedure been addressed?		\boxtimes		
13.3 Have data protection requirements been described?	\boxtimes			10

Comments:

Study is based on published information.

Section 14: Amendments and deviations	Yes	No	N/A	Section Number
14.1 Does the protocol include a section to document amendments and deviations?		\boxtimes		

Comments:

No amendments or deviations occurred.

Section 15: Plans for communication of study results	Yes	No	N/A	Section Number
15.1 Are plans described for communicating study results (e.g. to regulatory authorities)?	\boxtimes			
15.2 Are plans described for disseminating study results externally, including publication?	\boxtimes			
Commentes				

Comments:

Name of the main author of the protocol:

Date: 20/11/2018

